7.3. Demographic and Other Baseline Characteristics

Analysis population(s): FAS, safety analysis set

Analysis parameter: See Table 7.3

Analysis method: For each parameter, the number and proportion of subjects will be calculated, by group, for discrete data, and descriptive statistics will be calculated for continuous data. Additionally, if the FAS and the safety analysis set are the same, only the figures for the FAS will be output.

Table 7.3: Demographic and Other Baseline Characteristics/Analysis Parameters

Analysis Parameter		Data Category
Sex	Male, Female	Discrete
Age in months		Continuous
	≥ 2 and < 3 months, ≥ 3 months	Discrete
Concurrent illnesses	Yes, No	Discrete

Listings

Listing 7.3.1: Listing of Subject Backgrounds

Listing 7.3.2: Listing of Concomitant Medications

7.4. Status of Treatment Compliance

Analysis population(s): Safety analysis set

Analysis parameter: Presence or absence of receipt of a study drug injection

Analysis method: The number of subjects will be calculated for each number of injections (1, 2, 3), by group.

Listings

Listing 7.3: Listing of Doses of Investigational Product

7.5. Efficacy Analyses

7.5.1. Primary endpoints

Analysis population(s): FAS

Analysis parameter: The anti-PRP antibody seroprotection (antibody titer $\geq 1 \mu\text{g/mL}$) rate, and also the seroprotection rate for other antibodies (anti-diphtheria antibodies, anti-PT antibodies, anti-FHA antibodies, anti-tetanus antibodies, anti-poliovirus serotype 1 antibodies, anti-poliovirus serotype 2 antibodies, anti-poliovirus serotype 3 antibodies), at 4 weeks after the primary immunization

Analysis method: For each analysis parameter, the number of subjects, the number of subjects assessed for efficacy based on each antibody, the number of seroprotections, the seroprotection rate (%), and the two-sided, 95% confidence intervals will be calculated by group. Additionally, the 95% confidence interval of the difference between Group H and the control group in the seroprotection rate (%) for each type of antibody will be calculated using the Farrington-Manning method.

7.5.2. Secondary endpoints

7.5.2.1 Anti-PRP Antibody Seroprotection (titer $\geq 0.15 \mu\text{g/mL}$) Rate at 4 Weeks After the Primary Immunization

Analysis population(s): FAS

Analysis method: Anti-PRP antibody seroprotection at (titer $\geq 0.15 \mu\text{g/mL}$) rate at 4 weeks after the primary immunization

Analysis method: For each group, for each analysis parameter, the number of subjects, the number of subjects assessed for efficacy, the number of seroprotections, the seroprotection rate (%), and the two-sided 95% confidence intervals will be calculated. Additionally, the 95% confidence interval of the difference between Group H and the control group in the seroprotection rate (%) will be calculated using the Farrington-Manning method.

7.5.2.2 Antibody Titer Profiles

Analysis population(s): FAS

Analysis parameter: Titers of each type of antibody (anti-PRP antibodies, anti-diphtheria antibodies, anti-PT antibodies, anti-FHA antibodies, anti-tetanus antibodies, anti-poliovirus serotype 1 antibodies, anti-poliovirus serotype 2 antibodies, anti-poliovirus serotype 3 antibodies)

Analysis method: For each group, for each analysis parameter, the number of subjects, the number of subjects assessed for efficacy, the geometric mean, the geometric standard deviation, the two-sided 95% confidence interval of the geometric mean, and the minimum, median, and maximum values will be calculated. Additionally, the 95% confidence interval of the ratio of the geometric mean in Group H relative to that of the control group will be calculated at 4 weeks after the primary immunization.

Listings

Listing 7.5.2.2: Antibody Titer Listing

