### 9.2.3 Efficacy Endpoints

#### 9.2.3.1 Antibody Titers

The (sub)investigator or a clinical research coordinator will take blood samples at the following time points in order to measure the subject's antibody titers. More detailed information is provided in the separate "Clinical Study Testing Procedures." The (sub)investigator will record the days of blood sample collection (except for those in Cohort 3) in the case report form.

- (1) Sample Collection
  - 1) Times of blood sample collection, and volume of the sample collected, in Cohort 1
    - (a) Times of blood sample collection: Before the first vaccination with the investigational product, at Post-vaccination Examination 1, before the vaccination of the fourth dose of the investigational product, at Post-vaccination Examination 2, or at discontinuation (only when discontinuation occurs after the vaccination of the third or fourth dose of the investigational product)  
Volume of blood collected: Around 3 mL, as a rule
    - (b) Number of samples collected: 4
  - 2) Times of blood sample collection, and volume of the sample collected, in Cohort 2
    - (a) Times of blood sample collection: Before the first vaccination with the investigational product, at Post-vaccination Examination 1, or at discontinuation (only when discontinuation occurs after the vaccination of the third dose of the investigational product)  
Volume of blood collected: Around 3 mL, as a rule
    - (b) Number of samples collected: 2
  - 3) Times of blood sample collection, and volume of the sample collected, in Cohort 3

(a) Times of blood sample collection: Blood samples will be collected, as a rule, after 4 weeks have passed since the administration of the booster immunization.

Volume of blood collected: Around 3 mL, as a rule

(b) Number of samples collected: 1

4) Blood processing

The blood will be processed as described separately in the "Clinical Study Testing Procedures."

(2) Shipment of samples

The samples (serum) for antibody titer measurement will be collected by the antibody titer measurement sample transportation organization, and sent to the antibody titer measurement organization as described separately in the "Clinical Study Testing Procedures."

(3) Measurement parameters

Hib	Anti-PRP antibody concentration
Diphtheria	Anti-diphtheria antibody concentration
Pertussis	Anti-pertussis antibody concentration
	Anti-FHA antibody concentration
Tetanus	Anti-tetanus antibody concentration

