2.4. Assessment Time Point

The Cohort 2 assessment time points are shown below.

Day of consent	Visit 1		Visit 2		Visit 3		Visit 4		At discontinuation
	1st vaccination	2nd vaccination	3rd vaccination	Vaccination	Post-vaccination Examination 1				
Before	After	Before	After	Before	After	Before	After		
Allowable window	D1		Visit 1 + 3 - 8 weeks		Visit 2 + 3 - 8 weeks		Visit 3 + 4 - 6 weeks		
Written informed consent	•								
Investigation of subject background	•								
Examination	•		• ¹	•	• ¹	•	• ¹	•	•
Body temperature measurement (axillary)	•			•		•			
Investigational product vaccination		•			•		•		
Blood sampling (antibody titer)	•							•	• ²
Adverse events ³			↔						
e-Diary ⁴			•		•		•		

*1: Subjects will be asked to wait in the hospital for 30 minutes after receiving the investigational product, and will be examined 30 minutes after vaccination.

*2: Blood samples will be collected for antibody titer measurement only at discontinuation after the third dose of the investigational product has been administered.

*3: An investigation will be performed to confirm whether or not the subject experienced any adverse events during the period from Visit 1 to Visit 4 based on examination of the subject at the study visits and based on the subject's e-Diary.

*4: Every day until 14 days after each dose, if the subject's symptoms have not returned to normal by Day 14 after receiving the investigational product, then the subject will be asked to, as a rule, fill out the e-Diary until the symptoms return to normal.

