2.5. Sample Size Justification

○ Target sample size

Cohort 2: 340 subjects (BK1310 L group or H group: 170 subjects; control group: 170 subjects)

Rationale

Cohort 2 is positioned as a cohort for exploring the seroprotection rate in a phase 3 confirmatory study, and it was therefore decided that a sample size of 340 subjects (170 subjects per group) would allow for a proper assessment, taking into account the precision of estimating anti-PRP antibodies, etc.

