5.1. Efficacy Analysis Sets

The FAS will consist of all randomized subjects except for the following subjects.

- Subjects who did not take the investigational product at all
- Subjects for whom no antibody titer results at all could be obtained at 4 weeks after the primary immunization

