7. STATISTICAL METHODS

7.1. General Methods

7.1.1. Significance Level and Confidence Coefficient

Since this study is an exploratory study, no significance levels have been established. The confidence intervals will be two-sided confidence intervals, and the confidence coefficient will be 95%.

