7.1.6. Tabulation Time Points and Baselines

The tabulation time points will be displayed as shown in the table below. The baseline will be “Before the first dose at Visit 1.”

Table 7.1.5: Tabulation Time Points

Notation for Tabulation		Assessment Time Points in the Protocol
Assessment Time Point	Abbreviation	
Before the first vaccination	V1	Before the first dose at Visit 1
4 weeks after the primary immunization	V4	Post-vaccination examination at Visit 4, and at discontinuation

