7.5.3.2. Handling of Dropouts or Missing Data

Described in “5.1 Handling of Missing Values” of this document.

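### Cohort 2: the H/control geometric-mean ratio ignores the pre-dose-1 titer; the planned interval is valid, but adjusting for baseline would be a nearly free gain in precision

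*SAP*

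**What the plan says.** The Cohort 2 SAP, section 7.5.2.2, gives descriptive statistics for eight antibody titers in the FAS and adds one comparison between groups: "the 95% confidence interval of the ratio of the geometric mean in Group H relative to that of the control group will be calculated", at the visit four weeks after the third dose (V4). It names no model, covariate or interval method. Section 7.5.3.1 states that no covariate adjustment is planned.

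The baseline titer is already part of the design. Protocol 9.2.3.1 schedules Cohort 2 blood sampling "Before the first vaccination with the investigational product, at Post-vaccination Examination 1, or at discontinuation", and the schedule in SAP 2.4 shows the same draw. SAP 7.1.6 defines baseline as "Before the first dose at Visit 1". Table 7.5.3.8 uses the pre-dose titer, split at the reference value, as a subgroup factor.

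Other sections that bear on the point:
- SAP 7.1.1: "Since this study is an exploratory study, no significance levels have been established".
- SAP 5.1 excludes from the FAS "Subjects for whom no antibody titer results at all could be obtained at 4 weeks after the primary immunization". It does not require a baseline titer.
- SAP 6.1 treats unobtainable values as missing. SAP 6.3 replaces values below the limit of quantitation (LOQ) by half that limit, but only for descriptive statistics.
- SAP 7.5.3.2 refers the reader to "5.1 Handling of Missing Values", although section 5.1 defines the efficacy sets and missing values are in 6.1.

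**The concern.** With no significance level, the ratio is read through its interval, so the width of that interval is what the analysis delivers. In a randomized comparison, adjusting for a pre-treatment measurement of the same quantity removes the outcome variance that the measurement explains. Here the measurement is scheduled and paid for, yet the plan uses it only to cut the sample into subgroups. If baseline predicts the V4 titer, the planned intervals are wider than they need be.

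Only precision on a secondary, exploratory estimate is at stake. The primary seroprotection analysis (7.5.1) is untouched, and no planned conclusion becomes invalid if nothing changes.

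**Working it through.** **Inputs from the documents.** 170 infants per group, 1:1 (SAP 2.5); two-sided 95% intervals (7.1.1); log10 titers, log2 for polio (4.2). The plan gives no SD, correlation or target width for this ratio, and no inputs from which 340 could be reproduced.

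**Assumptions.** Normal log titers; the SD of log10 titer is 0.3, 0.5 or 0.7; r runs from 0 to 0.5. Only r² matters. The unadjusted interval is taken to be the usual two-sample t interval on the log scale, in keeping with 4.2.

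**Formulas.**
- Unadjusted half-width: t(338) × SD × √(2/170). With t(338) = 1.9670, √(2/170) = 0.10847 and SD 0.5 this is 0.1067, and 10^0.1067 = 1.278. The interval is the ratio times or divided by 1.278.
- Adjusted half-width ÷ unadjusted half-width: √(1 − r²) × √(1 + 1/336) × t(337)/t(338). At r = 0.3: 0.9539 × 1.0015 × 1.0000 = 0.955. With SD 0.5 the half-width becomes 0.1019, and 10^0.1019 = 1.264.

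| r | Width ratio | CI factor, SD 0.3 | SD 0.5 | SD 0.7 |
|---|---|---|---|---|
| unadjusted | 1 | 1.159 | 1.278 | 1.410 |
| 0 | 1.0015 | 1.159 | 1.279 | 1.411 |
| 0.1 | 0.9965 | 1.158 | 1.277 | 1.409 |
| 0.2 | 0.9813 | 1.156 | 1.273 | 1.401 |
| 0.3 | 0.9554 | 1.151 | 1.264 | 1.389 |
| 0.5 | 0.8673 | 1.136 | 1.237 | 1.348 |

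**Equivalent sample size.** Solving t(2m − 2) × √(2/m) = width ratio × t(338) × √(2/170) gives m = 176.5, 186.1 and 225.6 per group at r = 0.2, 0.3 and 0.5. That is about 7, 16 and 56 more infants per group in the unadjusted comparison. Break-even is at |r| of about 0.05, from √(1 − 1/(1 + 1/336)).

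**Baselines below the LOQ.** Simulation with 170 per group, SD 0.5, 4,000 runs per setting and low baselines set to half the limit. Width ratios by latent r:

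| Baselines below LOQ | r = 0.2 | r = 0.3 | r = 0.5 |
|---|---|---|---|
| 50% | 0.985 | 0.964 | 0.894 |
| 90% | 0.994 | 0.986 | 0.957 |
| 90%, and 5% missing (pooled-mean imputation) | 0.995 | 0.987 | 0.959 |

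In the last setting the ratio at r = 0 is 1.0016. With 98% or 99% below the limit and r = 0.3, the ratios are 0.996 and 0.9985: almost no gain, but no loss.

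**Missing baselines.** Dropping infants without a baseline can cost more than adjustment gains. At r = 0.2 with 5% missing, complete-case analysis gives 1.007 against 0.982 with pooled-mean imputation. At r = 0.3 with 10% missing, the figures are 1.008 and 0.960. The approximate complete-case break-even is |r| = √0.05 = 0.22 with 5% missing.

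**Coverage.** Adjusted and unadjusted intervals both covered between 94.2% and 95.7% in the settings simulated, so the planned interval is sound and the adjusted one is too.

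**The case against.** The strongest reply is that nothing is broken. The SAP considered adjustment and declined it, in an exploratory cohort with no significance level, for a ratio that the protocol does not ask for: Protocol 13.3.2.2 requires only the geometric means. The correlation is unknown, and infants with prior vaccination or disease are excluded, so many baselines may be low and uninformative. Cohort 1 was sampled at the same two time points, so the sponsor may have seen that baseline carries little information. All of this stands. It limits the priority but does not remove the asymmetry between a 0.15% cost and a possible gain of several percent.

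It is also fair that the sample-size rationale, "taking into account the precision of estimating anti-PRP antibodies, etc", most naturally concerns the seroprotection rate. It should not be read as a promise about the titer ratio, and the point does not need it.

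Three practical objections remain:
- **Transparency.** An adjusted ratio will generally differ from the ratio of the tabulated geometric means. True; this is why both should be reported.
- **Imputation.** Filling missing baselines departs from the default in Protocol 13.2.1 and SAP 6.1. The protocol states that default as a general rule, which leaves room for a stated exception.
- **Leverage.** If nearly all baselines are below the limit, a few detectable values have high leverage. The simulations at 98% and 99% show coverage of about 95% and no loss of width.

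**Conclusion.** The point holds as an efficiency improvement, not as an error. The planned ratio is unbiased and its interval valid, assuming the usual log-scale interval, since 7.5.2.2 names no method. With 170 per group, adjustment costs at most about 0.15% of interval width if baseline is uninformative. It gains about 2%, 4.5% and 13% at r = 0.2, 0.3 and 0.5, and between 0.6% and 4.3% over the same range if 90% of baselines are below the LOQ. The documents do not fix r, which may differ by antibody, so no single figure can be given and for some antibodies the gain may be close to nil. The change is nearly free only if missing baselines do not remove infants from the analysis. Priority is low.

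**What to change.** Before database lock, amend the Cohort 2 SAP as follows:

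- **7.5.2.2:** make the main ratio estimate for each antibody a linear model of log V4 titer on group and log baseline titer of the same antibody (log10; log2 for polio), with no other covariate. Back-transform the group contrast and its 95% interval. Keep the geometric means and the unadjusted ratio with its interval as supportive. If every baseline of an antibody is below the LOQ, omit the covariate.
- **6.1:** add one exception. A missing log baseline used as this covariate is set to the mean of the observed log baselines of that antibody, pooled across both groups, so that every FAS infant with a V4 titer stays in.
- **6.3:** extend the half-limit rule to the outcome and covariate of this model.
- **7.5.3.1:** replace the present statement with this one covariate for this one analysis.
- **7.5.3.2:** state the exception and correct the cross-reference from 5.1 to 6.1.

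If the sponsor regards the imputation exception as a change from Protocol 13.2.1, section 9 needs a line giving the reason, and Protocol 13.4 requires the same in the study report.

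The cost is wording, eight regressions and one extra ratio per antibody in the table. No new samples, visits or infants are needed. If the database is already locked, Protocol 13.4 requires the adjusted ratio to be reported as additional and kept distinct from the planned results.

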7.5.3. Issues in Statistical Analyses

7.5.3.1. Adjustments for Covariates

Not planned

7.5.3.2. Handling of Dropouts or Missing Data

Described in “5.1 Handling of Missing Values” of this document.

7.5.3.3. Interim Analyses and Data Monitoring

Not implemented

7.5.3.4. Multicenter Studies

Analysis population(s): FAS

Analysis parameter: Titers of each type of antibody (anti-PRP antibodies, anti-diphtheria antibodies, anti-PT antibodies, anti-FHA antibodies, anti-tetanus antibodies, anti-poliovirus serotype 1 antibodies, anti-poliovirus serotype 2 antibodies, anti-poliovirus serotype 3 antibodies)

Analysis method: For each site, for each group, for each analysis parameter, and for each time point, the number of subjects, the number of subjects assessed for efficacy, the geometric mean, the geometric standard deviation, and the minimum, median, and maximum values will be calculated.

7.5.3.5. Multiple Comparison/Multiplicity

Not applicable

7.5.3.6. Use of an “Efficacy Subset” of Patients

Not implemented

7.5.3.7. Active-Control Studies Intended to Show Equivalence

Not applicable

7.5.3.8. Analyses of Subgroups

7.5.3.8.1 Seroprotection Rates for Each Type of Antibody for Each Subgroup

Analysis population(s): FAS

Analysis parameter: The anti-PRP antibody seroprotection (titer $\geq 1 \mu\text{g/mL}$) rate, and also the antibody seroprotection rates for other antibodies (anti-diphtheria antibodies, anti-PT antibodies, anti-FHA antibodies, anti-tetanus antibodies, anti-poliovirus serotype 1 antibodies, anti-poliovirus serotype 2 antibodies, anti-poliovirus serotype 3 antibodies) at 4 weeks after the primary immunization

Analysis method: For the stratification factors shown in Table 7.5.3.8, for each group, the number of subjects, the number of subjects assessed for efficacy for each antibody, the number of seroprotections, the seroprotection rate (%), and the two-sided 95% confidence interval, will be calculated. Additionally, the 95% confidence intervals of the differences between Group H and the control group in the seroprotection rates will be calculated.

Table 7.5.3.8: Subgroups

Subgroups	
Sex	Male, Female
Age in months	≥ 2 and < 3 months, ≥ 3 months
Antibody titer before the first dose in the population in question	For each antibody titer: $<$ reference value, \geq reference value

7.5.3.8.2 Time Profiles of Each Type of Antibody, by Subgroup

Analysis population(s): FAS

Analysis parameter: Titers of each type of antibody (anti-PRP antibodies, anti-diphtheria antibodies, anti-PT antibodies, anti-FHA antibodies, anti-tetanus antibodies, anti-poliovirus serotype 1 antibodies, anti-poliovirus serotype 2 antibodies, anti-poliovirus serotype 3 antibodies)

Analysis method: For the subgroups shown in Table 7.5.3.8, for each group, for each analysis parameter, and for each time point, the number of subjects, the number of subjects assessed for efficacy, the geometric mean, the geometric standard deviation, the two-sided 95% confidence interval of the geometric mean, and the minimum, median, and maximum values will be calculated.

7.6. Safety Analyses

7.6.1. Adverse Events

The adverse event terms will be reclassified based on MedDRA/J Version 19.0.

7.6.1.1. Adverse Event Incidences

Analysis population(s): Safety analysis set

Analysis parameter: Adverse events (solicited adverse events, immediate reactions, other), adverse drug reactions (solicited adverse events, immediate reactions, other), serious adverse events, serious adverse drug reactions, adverse events leading to discontinuation, adverse drug reactions leading to discontinuation

Analysis method: For each group, the number and proportion (and 95% confidence interval thereof) of subjects experiencing each type of event will be calculated.

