2. STUDY OBJECTIVE AND STUDY DESIGN

2.1. Objectives

[figure not shown]
To investigate on an exploratory basis the safety of BK1310 and its immunogenicity against Hib in healthy infants, and to then investigate on an exploratory basis the efficacy and safety of BK1310 using simultaneous vaccination with ActHIB and Tetrabik as the control.

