7.1.3. Confidence Intervals (e.g., Seroprotection rate, Incidence)

When calculating the confidence intervals for the incidences of adverse events, etc., or the antibody seroprotection rates, Clopper & Pearson method will be used.

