7.6.1.2. Individual Adverse Events

Analysis population(s): Safety analysis set

Analysis parameter: Adverse events, adverse drug reactions, serious adverse events and reactions, adverse events and reactions leading to discontinuation

Analysis method: For each group, the numbers and proportions of subjects experiencing each type of event will be calculated by event category (solicited adverse events, immediate reactions, other) and by MedDRA/J SOC and PT. Group totals will be shown, as well. Additionally, adverse events and adverse drug reactions will be tabulated by event category (solicited adverse events, immediate reactions, other)

and severity (mild, moderate, severe). If the same subject experiences the same event multiple times at different levels of severity, the event will be tabulated using the highest reported level of severity.

Listings

Listing 7.6.1.2.1: Listing of Adverse Events

Listing 7.6.1.2.2: Listing of Adverse Drug Reactions

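### Cohort 2 safety is to be studied against the control, but no between-group estimate or interval is planned for any adverse event

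*SAP*

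**What the plan says.** The objective in section 2.1 of the Cohort 2 SAP is comparative for both halves. It is to "investigate on an exploratory basis the efficacy and safety of BK1310 using simultaneous vaccination with ActHIB and Tetrabik as the control"; Protocol section 2 agrees. Protocol 8.3.2 adds dummy bandages and keeps guardians from seeing the vaccination, so that local reactions are assessed without knowledge of group.

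The planned adverse event analyses in the Cohort 2 SAP are:

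- **7.6.1.1** (aggregate categories such as solicited, immediate, other, serious, leading to discontinuation): for each group, "the number and proportion (and 95% confidence interval thereof) of subjects experiencing each type of event will be calculated". Section 7.1.3 fixes the method: "When calculating the confidence intervals for the incidences of adverse events, etc., or the antibody seroprotection rates, Clopper & Pearson method will be used".
- **7.6.1.2** (individual events): for each group, "the numbers and proportions of subjects experiencing each type of event will be calculated by event category", by SOC and PT and by severity. No interval is named.
- **7.6.1.3 and 7.6.1.4** (by dose number, by subgroup, and pyrexia): counts and proportions only.

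Protocol 13.3.3 likewise asks for safety intervals by vaccination group and nothing between groups.

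Efficacy is treated differently. Section 7.5.1 adds "the 95% confidence interval of the difference between Group H and the control group in the seroprotection rate", by the Farrington-Manning method. Section 7.5.2.1 does the same for the lower anti-PRP threshold, and 7.5.2.2 adds a 95% interval for the ratio of geometric means.

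**The concern.** The same SAP quantifies the randomised contrast for one half of a joint objective and leaves the other half as two separate columns. The exploratory status does not explain the asymmetry. Section 7.1.1 says "Since this study is an exploratory study, no significance levels have been established", and that covers efficacy and safety alike, yet efficacy still gets between-group intervals. An interval for a difference is an estimate and needs no significance level.

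At stake is how the safety result is read. For the aggregate categories, the only precision on the page is one interval per group. Two such intervals can overlap when the interval for the difference clearly excludes zero, so a reader who compares them by eye may see less than the data show. For individual events, including pyrexia, no statement of precision is planned at all.

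**Working it through.** **Inputs.** Section 2.5: "Cohort 2: 340 subjects (BK1310 L group or H group: 170 subjects; control group: 170 subjects". Intervals are two-sided 95% (7.1.1), Clopper-Pearson within group (7.1.3). The documents give no adverse event rate, target difference, safety power or dropout allowance. I assume control rates of 2% to 70%, true differences of 5 to 20 points, and 170 evaluable per group. The 340 cannot be reproduced, because section 2.5 justifies it only by the precision of estimating anti-PRP antibodies, with no rate or width.

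**Two readings compared**, over all 171 × 171 outcomes of two independent binomials with n = 170:

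- Rule A: the two Clopper-Pearson 95% intervals do not overlap.
- Rule B: the 95% score interval for the difference excludes 0. At a difference of 0 the Farrington-Manning statistic is z = (p1 − p2) / √[p(1 − p) × 2/170], where p is the pooled proportion. The rule is |z| > 1.96.

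**One outcome by hand.** Control 68/170 = 40.0%, interval 32.6% to 47.8%. BK1310 94/170 = 55.3%, interval 47.5% to 62.9%. These overlap. Pooled p = 162/340 = 0.4765, standard error = √(0.4765 × 0.5235 × 2/170) = 0.0542, and z = 0.1529/0.0542 = 2.82, so the difference interval excludes 0. With control fixed at 68/170:

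- Rule A first fires at 95/170, a difference of 27/170 = 15.9 points.
- Rule B first fires at 86/170, a difference of 18/170 = 10.6 points. There pooled p = 154/340 = 0.4529, standard error = 0.0540 and z = 1.961. With the Miettinen-Nurminen variance it would be 87/170, or 11.2 points.

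**Detection where Rule B has 80% power:**

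| Control rate | BK1310 rate | Difference (points) | Rule A detects |
|---|---|---|---|
| 2% | 8.5% | 6.5 | 39.6% |
| 5% | 13.6% | 8.6 | 41.9% |
| 10% | 20.8% | 10.8 | 44.8% |
| 20% | 33.3% | 13.3 | 46.1% |
| 30% | 44.6% | 14.6 | 46.9% |
| 50% | 64.8% | 14.8 | 45.3% |
| 60% | 74.2% | 14.2 | 46.4% |
| 70% | 82.8% | 12.8 | 45.8% |

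A rough normal check supports this. With equal standard errors, non-overlap needs a difference √2 times larger: 1.96 × 1.414 = 2.77 standard errors of the difference. A difference with 80% power lies at 1.96 + 0.84 = 2.80, so about half the results would pass. Clopper-Pearson intervals are wider than normal ones, which brings this down to 40% to 47%.

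**Elsewhere on the power curve** (control rates 2% to 70%): where Rule B has 50% power, Rule A has 13% to 18%; at 90%, 58% to 64%; at 95%, 72% to 76%.

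**By fixed true difference** (control rates 5% to 70%), Rule A power divided by Rule B power is 0.16 to 0.26 at 5 points, 0.33 to 0.64 at 10, 0.58 to 0.93 at 15, and 0.83 to 1.00 at 20.

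**No true difference** (rates 5% to 70%): Rule A fires 0.25% to 0.40% of the time, Rule B about 5%.

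**The case against.** The strongest reply is that nothing is broken. Cohort 2 was changed from confirmatory to exploratory, no safety test is planned, and the SAP follows Protocol 13.3.3 faithfully. Group-wise description of adverse events is a coherent choice, and because counts and denominators are reported, any reader can compute the difference and its interval. All of this stands. It limits the point to presentation and interpretation: no planned test loses power, and no estimate is biased.

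It does not remove the asymmetry. Leaving the reader to calculate the contrast is not the same as planning it, and efficacy, equally exploratory, is not left to the reader.

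Three stronger readings are tempting and are not supported:

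- **That the plan judges safety by overlap.** No section prescribes this or any other rule for reading the safety intervals.
- **That the chance of seeing a difference is simply halved.** About half fits only differences detectable with roughly 80% power; across the assumed range the ratio runs from 0.16 to 1.00.
- **That an excess of fever would be dismissed because its intervals overlap.** Pyrexia is an individual event under 7.6.1.2 to 7.6.1.4, where no interval is planned. The gap for fever is that precision is absent altogether.

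**Conclusion.** The gap is real and rests on the documents alone: safety is to be investigated against the control, and no between-group estimate or interval is planned for any adverse event, while efficacy has both difference and ratio intervals.

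The size is conditional. If readers compare the 7.6.1.1 intervals by overlap, a difference detectable with 80% power by a difference interval is seen about 40% to 47% of the time. This assumes 170 evaluable infants per group and control rates of 2% to 70%, none of which the documents give as observed or expected. The loss is two thirds or more where the difference interval itself has about 50% power or less, and small for differences near 20 points. This is a cheap improvement to reporting, not an error that invalidates an analysis.

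**What to change.** In 7.6.1.1, and for the solicited (pre-specified) events in 7.6.1.2 including pyrexia, add the H minus control difference in proportions with a two-sided 95% interval. Use the Farrington-Manning method already named in 7.5.1, so that the SAP keeps one method for rate differences. Label the column descriptive and unadjusted for multiplicity. Because Protocol 13.3.3 mentions only intervals by group, record the addition and its reason in SAP section 9, as Protocol 13.4 provides for amendments before database lock.

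The cost is one column in existing tables and no new data. The downside is several unadjusted intervals, about 5% of which would exclude 0 by chance when there is no true difference. For the ten solicited terms in Protocol 9.2.4.2 (four local, six systemic) that is 10 × 0.05 = 0.5 expected. The label should tell readers to look at size and pattern, not at single exclusions of zero.
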